**8.3. Tertiary Efficacy Endpoint(s) and Analyses**

8.3.1. Between-treatment Group (Atropine Sulfate Ophthalmic Solution, 0.02% Versus Vehicle)  
Difference in the Proportion of Subjects' eyes who Show less than 0.5 D Myopia Progression (SER) From Baseline at the Month 24 and Month 12 visits

A tertiary analysis will be performed on between-treatment group (Atropine Sulfate Ophthalmic Solution, 0.02% Versus Vehicle) difference in the proportion of subjects' eyes who show less than 0.5 D myopia progression (SER) from baseline at the Month 24 and Month 12 visits. The analysis method will be the same as the primary efficacy analysis as described in 8.1.1 above using the updated statements:

*estimate '0.02% vs. Pbo Month 12' trtpn 0 1 -1 trtpn\*avisitn 0 0 0 0 0 0 1 0 0 0 0 0 -1 0 0 0 0 0*  
*trt01pn\*agegr1 0 0 0 1 0 -1;*

*estimate '0.02% vs. Pbo Month 24' trtpn 0 1 -1 trtpn\*avisitn 0 0 0 0 0 0 0 0 1 0 0 0 0 0 -1 0 0 0;*

Summary statistics and figure will be presented along with a full data listing by treatment group.

8.3.2. Between-treatment Group (Atropine Sulfate Ophthalmic Solution, 0.02% versus Vehicle)  
Difference in the Mean Change from Baseline in SER at the Month 24 and Month 12 Visits

A tertiary analysis will be performed on the between-treatment group (Atropine Sulfate Ophthalmic Solution, 0.02% versus vehicle) difference in the mean change from baseline in SER at the Month 24 and Month 12 visits. The analysis method will be the same as the secondary efficacy analysis as described in 8.2.1 above using the updated statements:

*estimate '0.02% vs. Pbo Month 12' trtpn 0 1 -1 trtpn\*avisitn 0 0 0 0 0 0 1 0 0 0 0 0 -1 0 0 0 0 0;*  
*estimate '0.02% vs. Pbo Month 24' trtpn 0 1 -1 trtpn\*avisitn 0 0 0 0 0 0 0 0 1 0 0 0 0 0 -1 0 0 0;*

Summary statistics and figure will be presented along with a full data listing by treatment group.

This document is confidential.

8.3.3. Between-treatment Group (Atropine Sulfate Ophthalmic Solution, 0.01% versus Vehicle)  
Difference in the Proportion of Subjects' Eyes Who Show less than 0.5 D Myopia  
Progression (SER) from Baseline at the Month 24 and Month 12 Visits

A tertiary analysis will be performed on the between-treatment group (Atropine Sulfate Ophthalmic Solution, 0.01% versus vehicle) difference in the proportion of subjects' eyes who show less than 0.5 D myopia progression (SER) from baseline at the 24 and Month 12 visits. The analysis method will be the same as the primary efficacy analysis as described in 8.1.1 above using the updated statements:

*estimate '0.01% vs. Pbo Month 12' trtpn 1 0 -1 trtpn\*avisitn 1 0 0 0 0 0 0 0 0 0 0 0 -1 0 0 0 0 0 ;*  
*estimate '0.01% vs. Pbo Month 24' trtpn 1 0 -1 trtpn\*avisitn 0 0 1 0 0 0 0 0 0 0 0 0 0 0 -1 0 0 0 ;*

Summary statistics and figure will be presented along with a full data listing by treatment group.

8.3.4. Between-treatment Group (Atropine Sulfate Ophthalmic Solution, 0.01% versus Vehicle)  
Difference in the Mean Change from Baseline in SER at the Month 24 and Month 12 Visits

A tertiary analysis will be performed on the between-treatment group (Atropine Sulfate Ophthalmic Solution, 0.01%) difference in the mean change from baseline in SER at the Month 24 and Month 12 visits. The analysis method will be the same as the secondary efficacy analysis as described in 8.2.1 above using the updated statements:

*estimate '0.01% vs. Pbo Month 12' trtpn 1 0 -1 trtpn\*avisitn 1 0 0 0 0 0 0 0 0 0 0 0 -1 0 0 0 0 0 ;*  
*estimate '0.01% vs. Pbo Month 24' trtpn 1 0 -1 trtpn\*avisitn 0 0 1 0 0 0 0 0 0 0 0 0 0 0 -1 0 0 0 ;*

Summary statistics and figure will be presented along with a full data listing by treatment group.

8.3.5. Between-treatment Group (Atropine Sulfate Ophthalmic Solution, 0.02% versus Vehicle)  
Difference in the Proportion of Subjects' Eyes who Show less than 0.75 D Myopia  
Progression (SER) From Baseline at the Month 36 Visit

A tertiary analysis will be performed on difference in the proportion of subjects' eyes who show less than 0.75 D myopia progression (SER) from baseline at the Month 36 visit. The analysis method will be the same as the primary efficacy analysis as described in 8.1.1 above.

Summary statistics and figure will be presented along with a full data listing by treatment group.

8.3.6. Between-treatment Group (Atropine Sulfate Ophthalmic Solution, 0.01% versus Vehicle)  
Difference in the Proportion of Subjects' Eyes who Show less than 0.75 D Myopia  
Progression (SER) From Baseline at the Month 36 Visit

A tertiary analysis will be performed on the between-treatment group (Atropine Sulfate Ophthalmic Solution, 0.01% versus vehicle) difference in the proportion of subjects' eyes who show less than 0.75 D myopia progression (SER) from baseline at the Month 36 visit. The analysis method will be the same as the primary efficacy analysis as described in 8.1.1 above using the updated statement:

*estimate '0.01% vs. Pbo Month 36' trtpn 1 0 -1 trtpn\*avisitn 0 0 0 0 1 0 0 0 0 0 0 0 0 0 0 -1 0 ;*

Summary statistics will be presented along with a full data listing by treatment group.

This document is confidential.

8.3.7. Between-treatment group (Atropine Sulfate Ophthalmic Solution, 0.02% versus Vehicle)  
Difference in the Time to Change from Baseline in Myopia Progression of -0.75 D SER

A tertiary analysis will be performed on the between-treatment group (Atropine Sulfate Ophthalmic Solution, 0.02% versus vehicle) difference in the time to change from baseline in myopia progression of -0.75 D SER.

The time to change in myopia progression of -0.75 D SER (days) = (first date with a change in myopia progression of -0.75 D or more – first date of treatment) +1. For subjects that were not observed to have a change in myopia progression of -0.75 D or more = Time to change in myopia progression of -0.75 D SER (days) [censored] = (Date of last known visit of Stage 1 – (first date of treatment) + 1.

The point estimate of the hazard ratios and the associated 95% confidence intervals will be obtained using the Cox proportional hazards regression model with fixed effects for treatment group, age at baseline, and baseline SER as covariates. An approximate Chi-square test based on Wald statistic will be used to compare treatment groups.

Summary statistics and associated survival curves (Kaplan-Meier estimates) will be presented along with a full data listing by treatment group.

Summary statistics will be presented along with a full data listing by treatment group.

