# Withdrawal of Subjects:

All subjects randomized into the study will be encouraged to complete all study assessments through the Month 48 Visit (End of Study), including subjects that cannot or do not wish to continue study treatment (withdraw consent/assent from study treatment but are willing to continue study visits).

The following are the criteria for considering withdrawal from the study (Study discontinuation prior to Visit Month 48):

- Withdrawal of subject consent/assent to continue with study visits.
- If the site and/or the overall study is terminated for any reason.
- The Investigator considers it is in the best interest for the subject to leave the study. This may include the development of damage to the cornea (Section 8.5 Discontinuation of Study Medication).

If a subject withdraws from the study, the reason for the subject's withdrawal will be recorded in the electronic case report form (eCRF).

If a subject is discontinued from study medication before the Month 48 visit, then all Month 48 procedures should be performed at the visit the subject discontinues study medication. The subject should continue in the study off study medication. Subjects should be encouraged to return for the 6 Month interval visits; however, returning for the 12 Month interval visits is essential. Subjects discontinuing study medication prior to Month 36 would continue to be seen for scheduled visits (at 6 Month or 12 Month intervals as noted above) until they reach the Month 36 interval.

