### **3.8. Study Procedures and Flowchart**

During Stage 1, office visits will occur at Screening/Baseline, Months 3, 6, 9, 12, 15, 18, 21, 24, 27, 30, 33, and 36.

During the Three-Month Visits (Months 3, 9, 15, 21, 27, 33), subjects and their parent/guardian will return to the study site with their randomized study medication for an evaluation of treatment adherence. While it is preferred that the subject attend every visit, the parent/guardian may attend a 3-month visit without the subject if necessary. Sites will update concomitant medications, conduct AE assessment, dispense study medication, and perform treatment adherence assessment (i.e., study medication accountability).

During the Stage 1 Six-Month Visits (Months 6, 12, 18, 24, and 30), subjects and their parent/guardian will return to the study site with their randomized study medication for an evaluation of treatment adherence. Subjects will undergo a measurement of height (yearly), weight (yearly), HR, BCVA measurement (distance and near), photopic pupil size measurement, slit-lamp examination (SLE), tonometry, dilated fundus examination (yearly), cycloplegic autorefraction, axial length and, if possible, crystalline lens thickness. Sites will update concomitant medications, conduct AE assessment, dispense study medication, and perform treatment adherence assessment.

During the Month 36 visit, subjects and their parent/guardian will return to the study site with their randomized study medication for an evaluation of treatment adherence. Subjects will undergo a measurement of height, weight, HR, BCVA measurement (distance and near), photopic pupil size measurement, SLE, tonometry, dilated fundus examination, cycloplegic autorefraction, axial length and, if possible, crystalline lens thickness. Subjects will then be re-randomized. Sites will update concomitant medications, conduct AE assessment, dispense randomized study medication for the randomized crossover stage (Stage 2), and perform treatment adherence assessment.

For the Stage 1 Telephone Checks - (Months 1, 2, 4.5, 7.5, 10.5) sites will contact subjects or their parent/guardian by telephone at the end of Month 1 and Month 2 and then midway between office visits during the initial year of the study to collect information regarding AEs and treatment adherence. Telephone checks can be continued or reinstated at any time during the study to assist with maintaining protocol and treatment adherence.

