## 8.1. Primary Efficacy Endpoint and Analysis

### 8.1.1. Primary Efficacy Endpoint

The primary efficacy endpoint is the between-treatment group (Atropine Sulfate Ophthalmic Solution, 0.02% versus Vehicle) difference in the proportion of subjects' eyes who show less than 0.5 D myopia progression (SER) from baseline at the Month 36 visit.

Spherical equivalent refraction will be measured using cycloplegic autorefractometry at Months 6, 12, 18, 24, 30, and 36. Subjects' eyes will be determined at each visit if they have a less than 0.5 D myopia progression (SER). All data collected through Month 36 will be used, regardless of when treatment is stopped. There will be no imputation for missing data; analysis will be conducted as observed.

The primary analysis will be performed using a Mixed Model based on the binomial distribution using a logit link function. Progression as the dependent variable, subject, treatment, visit, eye (left or right) and baseline age group (as randomized) and SER (as randomized) as independent variables and treatment by visit interaction term included. Random intercepts for subject and eye within subject will be included using variance components and compound symmetry covariance structures, respectively. The primary analysis will be performed using the mITT analysis set assuming data is missing at random.

```
proc glimmix data=master empirical method=quad;  
  class subjid trtpn(ref='0') avisitn eye agegr1 sergr1;  
  model eff(event='1') = trtpn avsitn eye agegr1 sergr1 trtpn*avisitn / dist=bin link=logit solution or;  
  nloptions tech=nrridg maxiter=25;  
  random intercept / subject=subjid type=vc;  
  random intercept / subject=eye(subjid) type=cs;  
  estimate '0.02% vs. Pbo Month 36' trtpn 0 1 -1 trtpn*avisitn 0 0 0 0 0 0 0 0 0 0 1 0 0 0 0 0 -1;
```

The absolute risk difference and associated Wald 95% CI will also be presented at Month 36 using the following frequency procedure.

```
proc freq data=dat order=data;  
  tables trtpn*eff / riskdiff(equal cl=wald);
```

Counts and percentage of subject' eyes progressing at each visit for each stage will be summarized. For the primary endpoint and associated secondary endpoints, Odds Ratios, 95% confidence interval (CI), and p-value will be provided along with an accompanying figure.

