- Medical reason (AE)
- Physician decision to discontinue treatment
- Death
- Lack of efficacy

Non-treatment related missing data are data missing because a subject terminates the study prior to the Month 36 visit for the following termination reasons:

- Visit missed or telemedicine visit due to COVID-19
- Sponsor terminated study
- Lost to follow-up
- Pregnancy
- Other

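### Time to -0.75 D progression (SAP 8.3.7, 8.3.8) is censored at the last visit of any kind, not the last refraction, so some unassessed time counts as event-free; the effect is small

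*SAP*

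**What the plan says.** SAP 8.3.7 dates the event at the "first date with a change in myopia progression of -0.75 D or more". A child without an event is censored at the "Date of last known visit of Stage 1", and nothing requires that refraction was measured there. SAP 8.3.8 applies the same method to 0.01% versus vehicle. The analysis is a Cox model with a Wald test, with Kaplan-Meier curves alongside.

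On refraction, SAP 8.1.1 states: "Spherical equivalent refraction will be measured using cycloplegic autorefractometry at Months 6, 12, 18, 24, 30, and 36". On visits, SAP 3.8 states that in Stage 1 "office visits will occur at Screening/Baseline, Months 3, 6, 9, 12, 15, 18, 21, 24, 27, 30, 33, and 36". For the visits at Months 3, 9, 15, 21, 27 and 33 it lists only this: "Sites will update concomitant medications, conduct AE assessment, dispense study medication, and perform treatment adherence assessment (i.e., study medication accountability". It adds that "the parent/guardian may attend a 3-month visit without the subject if necessary".

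Two other provisions matter. A child who stops study medication should have the end-of-study procedures, which include autorefraction, at that visit (Protocol synopsis, Early Termination Visits; Table 2, note b). The SAP's sensitivity analysis of the primary endpoint (8.1.3) also names, among the reasons for non-treatment-related missing data, "Visit missed or telemedicine visit due to COVID-19".

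**The concern.** Kaplan-Meier and Cox methods treat all time up to censoring as time in which the child was known to be event-free. That holds only if an event in that time would have been seen. Here a child can stay in contact with the site without being refracted, and the rule keeps that child in the risk set as a non-progressor.

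Two results are exposed. The progression-free curves are raised in any arm with such children, whether or not the arms are balanced. The hazard ratio is affected only if the share of unassessed follow-up differs between arms; it then moves in favour of the arm with more of it.

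**Working it through.** The plan gives no event count, hazard ratio or power for this endpoint, so there is no stated figure to reproduce.

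**1. Visits.** Post-baseline Stage 1 office visits: 12. With refraction: Months 6, 12, 18, 24, 30 and 36, so 6. Without: 12 − 6 = 6, or 50%.

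**2. Who is affected.**
- Refracted at Month 36 or at an exit visit: last visit and last refraction coincide; no effect.
- One refraction missed but a later one done: neither rule censors at the gap; no effect.
- Lost after a 3-month visit with no exit refraction: about 3 months (about 91 days) credited unassessed.
- Later 6-month refractions missed, but contact continues: 6 months or more credited unassessed.

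**3. Mechanism.** At an event time with *n* children at risk, *d* events and *u* children who have no refraction then or later, the Kaplan-Meier factor is 1 − d/n under the plan's rule and 1 − d/(n − u) if those *u* children leave at their last refraction. On schedule, events occur only at refraction visits. Moving a censoring date from Month 30 to Month 33 therefore passes no event time, whereas moving it from Month 24 to Month 33 passes the Month 30 risk set. The 3-month visits alone should do little; missed 6-month refractions should do more.

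**4. Simulation with a treatment effect.** From the documents: 125 vehicle and 186 on 0.02%; 27% Stage 1 drop-out; visits every 3 months ± 2 weeks; refraction every 6 months. Assumed: 70% of vehicle children progress by Month 36; hazard ratio (HR) 0.70; exit refraction in 0 to 100% of drop-outs; 0 to 20% of 6-month visits without refraction. Unadjusted Cox model, 600 runs (Kaplan-Meier on the first 100). Paired figures are last visit / last refraction; KM is event-free at Month 33.

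| Exit refraction | 6-month refractions missed | Extra person-time | HR | KM vehicle | KM 0.02% |
|---|---|---|---|---|---|
| 100% | 0 | 0.0% | 0.6975 / 0.6975 | 0.351 / 0.351 | 0.488 / 0.488 |
| 0% | 0 | 1.3% | 0.6983 / 0.6986 | 0.356 / 0.352 | 0.493 / 0.488 |
| 0% | 10% | 2.9% | 0.6988 / 0.6988 | 0.366 / 0.355 | 0.501 / 0.491 |
| 0% | 20% | 5.1% | 0.6999 / 0.7005 | 0.380 / 0.358 | 0.515 / 0.495 |
| 100% | 20% | 2.4% | 0.6989 / 0.6991 | 0.370 / 0.357 | 0.506 / 0.495 |

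Unequal drop-out, no exit refraction, 20% missed:
- Vehicle 35%, 0.02% 20%: HR 0.6939 / 0.6851 (ratio 1.013); vehicle KM 0.379 / 0.354, a gap of 0.025; person-time +5.0%.
- Vehicle 20%, 0.02% 35%: HR 0.7040 / 0.7140 (ratio 0.986); person-time +5.3%.

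These are differences between the two rules, not distances from the truth. The assumed event-free proportions at Month 30 are 0.3^(30/36) = 0.367 (vehicle) and 0.3^(0.7 × 30/36) = 0.495 (0.02%). With 20% missed and no exit refraction, the plan's rule is above both (by 0.013 and 0.020). With none missed, both rules sit slightly below 0.367 and the plan's rule is not the worse one.

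Month 36 readings from these runs show gaps of up to 0.182 − 0.137 = 0.045, but I do not use them. Completers leave the risk set at their own Month 36 date while others in the window still have events, so both rules fall far below the assumed 0.30.

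**5. Simulation with no treatment effect.** Assumed: mean progression about 0.5 D/year, visits on schedule, and a share of children last refracted at Month 18, 24 or 30 but with visits to Month 36.
- Share 15%: Month 36 KM 0.184 / 0.158, a gap of 0.026.
- Shares 15% vs 5%: HR 0.980 / 1.012, ratio 0.968.
- Shares 20% vs 10%: HR 0.961 / 0.990, ratio 0.971.
- Shares 10% vs 5%: HR 0.983 / 1.000, ratio 0.983.
- Equal shares: HR unchanged.

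**6. Against sampling error.** In step 4 the standard error of the log HR is about 0.16; ln(0.986) = −0.014, about 0.09 standard errors. In step 5 it is about 0.11 at 186 vs 125; ln(0.968) = −0.032, about 0.3 standard errors.

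**The case against.** The strongest defence is that the plan leaves little room for harm. Child and parent must both attend every 6-month visit, where refraction is done. Children who stop medication should be refracted at that visit. The 3-month visits alone barely move the results. The COVID-19 item sits in a list of reasons for children who terminate before Month 36; it does not show unrefracted visits continuing to Month 36, nor say that a remote contact counts as a Stage 1 visit. Treatment is masked, so a large imbalance between arms is not expected. The endpoint is tertiary, and the binary 0.75 D analyses in 8.3.5 and 8.3.6 do not use this rule.

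Most of this stands, and it is why the effect is small. It does not repair the rule: no passage ties censoring to a refraction, children lost to follow-up may have no exit refraction, and the SAP itself foresees missed and remote visits.

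Three stronger readings are tempting but not supported.
- A reader might infer that distant families in general are seen by telephone. The allowance covers only sponsor-approved transfer subjects living more than 150 miles from the new site, and only 3-month visits.
- A reader might infer that children off drug gain more unassessed time, because the Protocol says "Subjects should be encouraged to return for the 6 Month interval visits; however, returning for the 12 Month interval visits is essential". Those visits include refraction, so a child seen yearly has the same last visit and last refraction. Longer gaps make event dates coarser. That is interval censoring, which this change does not address.
- A reader might take 3% as the expected bias in the hazard ratio. It needs an assumed 2:1 or 3:1 imbalance in unrefracted follow-up, for which the documents give no basis.

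**Conclusion.** The point holds as a minor defect of definition. The rule as written counts some time in which progression could not be detected as event-free, but only for children without an observed event whose last Stage 1 contact had no refraction.

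Under the assumed shares, person-time is overstated by 0 to about 5%, and Kaplan-Meier progression-free estimates are up to about 0.025 higher than with censoring at the last refraction, mainly when 6-month refractions are missed. The hazard ratio changes by less than 0.1% with equal drop-out, by up to about 1.4% with drop-out of 35% versus 20%, and by about 3% only under the larger assumed imbalance. The progression rate, treatment effect, missed-refraction share and exit-refraction share are all assumptions. No primary or secondary conclusion depends on this endpoint, which lies outside the fixed sequence in SAP section 8.

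**What to change.** In SAP 8.3.7, replace "Date of last known visit of Stage 1" with: date of the last Stage 1 cycloplegic autorefraction. Add that a child with no post-baseline refraction is censored at Day 1. Section 8.3.8 inherits the change.

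The cost is one phrase and one derivation, with no new data and slightly shorter follow-up for some censored children. If every child without an event was refracted at the last Stage 1 visit, the results do not change.

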8.3.8. Between-treatment Group (Atropine Sulfate Ophthalmic Solution, 0.01% versus Vehicle)  
Difference in Time to Change from Baseline in Myopia progression of -0.75 D SER

A tertiary analysis will be performed on the between-treatment group (Atropine Sulfate Ophthalmic Solution, 0.01% versus vehicle) difference in the time to change from baseline in myopia progression of -0.75 D SER. The analysis method will be the same as the tertiary efficacy analysis as described in 8.3.7 above.

Summary statistics will be presented along with a full data listing by treatment group.

8.3.9. Between-treatment Group (Atropine Sulfate Ophthalmic Solution, 0.02% versus Vehicle)  
Difference in the Number of New Prescriptions Given After the Start of Treatment Due to Progression through the Month 36 visit

A tertiary analysis will be performed on the between-treatment group (Atropine Sulfate Ophthalmic Solution, 0.02% versus vehicle) difference in the number of new prescriptions given after the start of treatment due to progression through the Month 36 visit. The analysis method will be performed using the Cochran-Mantel-Haenszel row mean scores (ANOVA) statistic using the statement.

```
proc freq data=xxxx;  
  tables Treatment*Prescriptions /cmh noprint;  
run;
```

Summary statistics will be presented along with a full data listing by treatment group.

This document is confidential.

8.3.10. Between-treatment Group (Atropine Sulfate Ophthalmic Solution, 0.01% versus Vehicle) Difference in the Number of New Prescriptions Given After the Start of Treatment Due to Progression through the Month 36 visit

A tertiary analysis will be performed on the between-treatment group (Atropine Sulfate Ophthalmic Solution, 0.01% versus vehicle) difference in number of new prescriptions given after the start of treatment due to progression through the Month 36 visit. The analysis method will be performed using the Cochran-Mantel-Haenszel row mean scores (ANOVA) statistic using the statement.

```
proc freq data=xxxx;  
  tables Treatment*Prescriptions /cmh noprint;  
run;
```

Summary statistics will be presented along with a full data listing by treatment group.

8.3.11. Between-treatment Group (Atropine Sulfate Ophthalmic Solution, 0.02% Versus Vehicle) Difference in the Proportion of Subjects who Progressed to High Myopia (SER -6.00 D or more myopic) at the Month 36 Visit

A tertiary analysis will be performed on the between-treatment group (Atropine Sulfate Ophthalmic Solution, 0.2% versus vehicle) difference in the proportion of subjects who progressed to high myopia (SER -6.00 D or more myopic) at the Month 36 visit. Progression to high myopia is defined as either of a subject's eyes progressed to high myopia at any time during a visit window. The analysis method will be the same as the analysis as described in 8.3.12 below. Results will be presented as overall results and by baseline myopia stratification.

Summary statistics will be presented along with a full data listing by treatment group.

8.3.12. Between-treatment Group (Atropine Sulfate Ophthalmic Solution, 0.01% versus Vehicle) Difference in the Proportion of Subjects who Progressed to High Myopia (SER -6.00 D or more myopic) at the Month 36 Visit

A tertiary analysis will be performed on the between-treatment group (Atropine Sulfate Ophthalmic Solution, 0.1% versus vehicle) difference in the proportion of subjects who progressed to high myopia (SER -6.00 D or more myopic) at the Month 36 visit. Progression to high myopia is defined as either of a subject's eyes progressed to high myopia at any time during a visit window.

Results will be presented as results and by baseline myopia stratification. The overall analysis will be performed using a Mixed Model based on the binomial distribution using a logit link function. Progression as the dependent variable, subject, treatment, visit, and baseline age group (as randomized) and SER (as randomized) as independent variables, treatment by visit, treatment by SER (as randomized) and treatment by visit by SER (as randomized) interaction terms included. Random intercepts for subject will be included using variance components. The analysis will be performed using the mITT analysis set assuming data is missing at random.

```
proc glimmix data=master empirical method=quad;  
  class subjid trtpn(ref='0') avisitn agegrp1 sergrp1;  
  model eff(event='1') = trtpn avsitn agegrp1 sergrp1 trtpn*avisitn trtpn*sergrp1 trtpn*avisitn*sergrp1 /  
  dist=bin link=logit solution or;  
  random intercept / subject=subjid type=vc;  
  estimate '0.02% vs. Pbo Month 36' trtpn 0 1 -1 trtpn*avisitn 0 0 0 0 0 0 0 0 0 0 0 0 1 0 0 0 0 0 -1;
```

This document is confidential.

*estimate '0.02% vs. Pbo Month 36 Low ' trtpn 0 1 -1 trtpn\*avisitn 0 0 0 0 0 0 0 0 0 0 0 0 1 0 0 0 0 0 -1  
trtpn\*avisitn\*blmymop 0 1 0 0 0 0 0 -1 0;*

*estimate '0.02% vs. Pbo Month 36 High ' trtpn 0 1 -1 trtpn\*avisitn 0 0 0 0 0 0 0 0 0 0 0 0 1 0 0 0 0 0 -1  
trtpn\*avisitn\*blmymop 0 1 0 0 0 0 0 -1;*

Summary statistics will be presented along with a full data listing by treatment group.

